5.4 Exclusion Criteria

Patients eligible for this study must not meet any of the following criteria:

Proprietary Information of MD Anderson

Protocol 2020-1241

19 October 2022

1. The patient has CNS involvement. If the patient fulfills the following 3 criteria, she/he is eligible for the study:
 - a. Completed prior therapy (including radiation and/or surgery) for CNS metastases, and
 - b. CNS tumor is radiologically stable for ≥ 28 days prior to study start, and
 - c. The patient is not receiving steroids and enzyme-inducing antiepileptic medications for brain metastases.
2. Patients with HER2 positive breast cancer.
3. Patients must be ≥ 4 weeks or at least 5 half-lives beyond treatment with any chemotherapy or other investigational therapy including hormonal, biological, or targeted agents at the time of treatment initiation.
 - NOTE: If the patient received major surgery, she/he must have recovered adequately from the toxicity and/or complications from the intervention prior to starting the study treatment.
4. For cohorts 1 and 2 prior treatment with fulvestrant or any PI3Ki.
5. Known hypersensitivity to copanlisib or fulvestrant, or any of the excipients of copanlisib or fulvestrant.
6. Concomitant use of strong CYP3A4 inducers (e.g., rifampicin, phenytoin, carbamazepine, phenobarbital, St. John's wort) or inhibitors (e.g., ritonavir, saquinavir, nelfinavir, boceprevir, telaprevir, ketoconazole, omeprazole). Use of strong inhibitors and/or inducers of CYP3A4 is not permitted from Day -14 of Cycle 1 until the end of the study treatment. (See **Appendix F: Strong Inhibitors or Strong Inducers of CYP3A4**)
7. The patient is currently receiving warfarin or other coumarin derived anticoagulants for treatment, prophylaxis, or otherwise. Therapy with heparin, low molecular weight heparin, fondaparinux, or direct oral anticoagulants such as rivaroxaban or apixaban is allowed.
8. Known additional malignancy that is progressing or requires active treatment.
9. History or current evidence of any condition, therapy, or laboratory abnormality that might confound the results of the study, interfere with the patient's participation for the full duration of the study or is not in the best interest of the patient to participate, in the opinion of the treating investigator.
10. Known psychiatric or substance abuse disorders that would interfere with cooperation with the requirements of the study.
11. Known history of human immunodeficiency virus infection.
12. History or current symptomatic pneumonitis.
13. Has clinically significant, uncontrolled heart disease and/or recent cardiac events, including any of the following:

Proprietary Information of MD Anderson

Protocol 2020-1241

19 October 2022

- a. History of angina pectoris, symptomatic pericarditis, or myocardial infarction within 12 months prior to study entry
- b. History of documented congestive heart failure (New York Heart Association functional classification III-IV)
- c. Documented cardiomyopathy
- d. History of any cardiac arrhythmias, e.g., ventricular, supraventricular, nodal arrhythmias, or conduction abnormality in the previous 12 months
- e. Uncontrolled hypertension defined by a systolic blood pressure (BP) ≥ 140 mmHg and/or diastolic BP ≥ 90 mmHg, with or without antihypertensive medication over the course of one clinic visit at intervals of ≥ 30 minutes. Initiation or adjustment of antihypertensive medication(s) is allowed prior to screening.

14. Type 1 diabetes mellitus.

[figure not shown]
15. Uncontrolled type 2 diabetes mellitus.

16. Positive cytomegalovirus (CMV) polymerase chain reaction (PCR) test at baseline.

17. Active hepatitis B virus (HBV; chronic or acute; defined as having a known positive hepatitis B surface antigen [HbsAg] test at the time of screening) or hepatitis C infection requiring treatment.

- Participants with past HBV infection or resolved HBV infection (defined as the presence of hepatitis B core antibody [HbcAb] and absence of HbsAg) are eligible if HBV DNA is negative.
- Participants with positive for hepatitis C virus (HCV) antibody are eligible only if PCR is negative for HCV RNA.

6 STUDY TREATMENT

[figure not shown]
Proprietary Information of MD Anderson

Protocol 2020-1241

19 October 2022

consent, or discontinuation from the study treatment for any other reason. Patients who develop disease progression as centrally assessed according to the RECIST v1.1 criteria, as appropriate, may be allowed to continue treatment if the patient is benefitting from the study treatment in the opinion of the investigator, the patient is clinically asymptomatic, and continued study treatment is approved by the sponsor.

Dose escalation will not be allowed for progressive disease.

6.1.1 Copanlisib dosing requirements for pre-dose glucose levels

Copanlisib should be administered if pre-glucose level is <160 mg/dL for fasting, or <200 mg/dL for non-fasting participants. Fasting status refers to a ≥ 8 hours fast. Non-fasting status includes any caloric intake, such as meals, as well as juice, snacks, and other caloric intake not consistently called a meal.

For diabetic participants, who take insulin treatment at any cycle visit, timing and content of meal intake will be managed by the investigator. Consultation with treating physician or endocrinologist is advised.

Because of inhibitory effect on PI3K α -isoform, which is implicated in insulin metabolism, copanlisib infusions may be associated with temporary increase in blood glucose. Addition of a meal in close proximity to copanlisib infusion may exacerbate glucose increase.

On infusion days, a low calorie or low carbohydrate diet is recommended. The timing and content of caloric meal intake and additional glucose testing (if clinically indicated) is managed and monitored by the investigators based on glucose response patterns during prior intervention days. Consultation with endocrinologist is advised.

All glucose measurements done at the site, oral glucose lowering medication and/or insulin administration, if applicable, fasting/non-fasting status and meal intake timing on infusion days will be collected as part of the clinical source documentation.

[figure not shown]
Proprietary Information of MD Anderson

Protocol 2020-1241

19 October 2022

6.2 Dose Modification

Any toxicity observed during the study can be managed by interruption of the dose of study treatments or dose reductions. Repeated dose interruptions are allowed as required, for a maximum of 4 weeks on each occasion. Where toxicity recurs following re-challenge with study drugs, and where further dose interruption is considered inadequate for toxicity management, then withdrawal is indicated.

[figure not shown]
If either of the study drugs or both drugs need to be held due to AEs, then the study drug deemed to be responsible for the AE will be held until AE resolves to grade 1 or baseline. When copanlisib or fulvestrant dosing is interrupted, either the patient must recover completely, or the toxicity must revert to NCI CTCAE \leq Grade 1 or baseline before restarting study treatment. Patients whose NCI CTCAE Grade 3 or 4 event does not resolve to \leq 1Grade or baseline within 4 weeks should be withdrawn from the study. When a patient withdraws prior to study completion, all applicable activities scheduled for the final study visit should be performed at the time of withdrawal. Any AEs that are present at the time of withdrawal should be followed until \leq Grade 1 or baseline.

Proprietary Information of MD Anderson

Protocol 2020-1241

19 October 2022

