6.3 Toxicity Management

All dose modifications should be documented, including the approach taken and a clear rationale for the need for modification. For dose modification, the investigator must first assess if the toxicity is considered at least possibly related to the study treatment and must then apply the dose modification guidelines accordingly. Below are dose delay and management tables for the study drugs. These algorithms should be followed unless there are specific clinical circumstances for which the treating physician decides an alternative treatment approach is clinically appropriate. Consultation with the study chair is recommended.

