6.3.1 Copanlisib toxicity management

Table 5: Management of Nausea/vomiting

Toxicity	Action to be Taken
CTCAE Grade 1	No change in dose
CTCAE Grade 2	Hold* until \leq Grade 1. No change in dose
CTCAE Grade 3	Hold* until \leq Grade 2. Resume at one dose level lower, if indicated.**
CTCAE Grade 4	Off copanlisib treatment

*Patients requiring a delay of >2 weeks may go off protocol therapy.
**Patients requiring >2 dose reductions should go off protocol therapy.

Recommended management: Antiemetics

Table 6: Management of Diarrhea

Toxicity	Action to be Taken
CTCAE Grade 1	No change in dose
CTCAE Grade 2	Hold* until \leq Grade 1. No change in dose
CTCAE Grade 3	Hold* until \leq Grade 2. Resume at one dose level lower, if indicated.**
CTCAE Grade 4	Off copanlisib treatment

*Patients requiring a delay of >2 weeks may go off protocol therapy.
**Patients requiring >2 dose reductions should go off protocol therapy.

Proprietary Information of MD Anderson

Protocol 2020-1241

19 October 2022

Recommended management: Loperamide antidiarrheal therapy

Dosage schedule: 4 mg at the first onset, followed by 2 mg with each loose motion until diarrhea-free for 12 hours (maximum dosage: 16 mg/24 hours)

Adjunct anti-diarrheal therapy is permitted and should be recorded when used.

Table 7: Management of thrombocytopenia

Toxicity	Action to be Taken
CTCAE Grade 1	No change in dose
CTCAE Grade 2	No change in dose
CTCAE Grade 3	Hold* until \leq Grade 1. Resume at one dose level lower, if indicated. **
CTCAE Grade 4	Off copanlisib treatment

*Patients requiring a delay of >2 weeks may go off protocol therapy.

**Patients requiring >2 dose reductions should go off protocol therapy.

Table 8: Management of Neutropenia

Toxicity	Action to be Taken
CTCAE Grade 1	No change in dose
CTCAE Grade 2	No change in dose
CTCAE Grade 3	Hold* until \leq Grade 2. Resume at one dose level lower, if indicated. **
CTCAE Grade 4	Off copanlisib treatment

*Patients requiring a delay of >2 weeks may go off protocol therapy.

**Patients requiring >2 dose reductions should go off protocol therapy.

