6.3.1.4 Dermatologic toxicity

The recommendations for dose modifications in cases of dermatologic toxicity are outlined in **Table 14**. If these recommendations are not followed, the rationale for other measures will be documented in detail in the participant's medical record.

Table 13: Dose modification of copanlisib for dermatologic toxicity

Toxicity (CTCAE grade)	Occurrence	For current course of therapy	For next course of therapy
Grade 1 and 2	Any appearance	No change	No change
Grade 3 ^a	1 st appearance	Interruption until Grade ≤ 2	Decrease by one dose level ^b
	2 nd appearance	Interruption until Grade ≤ 2	Decrease by one dose level ^b
	3 rd appearance	Permanent discontinuation	—
Grade 4	1 st appearance	Permanent discontinuation	—

Abbr.: CTCAE = Common terminology criteria of adverse events.

a. Despite maximum supportive therapy.

b. The lowest dose level is 30 mg; if a participant is already on the 30 mg dose level study intervention and meets criteria for further decrease of dose, copanlisib will be discontinued permanently.

If dermatologic changes occur, the participant should be treated quickly and aggressively. **Table 15** can be used as guidance.

Proprietary Information of MD Anderson

Protocol 2020-1241

19 October 2022

Table 14: Guidance on treatment of skin toxicities

MILD (CTCAE Grade 1)	
Dry Skin /	Emollients, - Eucerin or Aquaphor plus gentle soaps
Fissures	(Dove, Cetaphil, Basis), use fragrance free detergents
Rash	Topical hydrocortisone 2.5% and/or clindamycin 1% gel plus doxycycline 100 mg b.i.d. or Minocycline 100 mg b.i.d.
Nail Changes	Moisturizers
Pruritus	Pramoxine 1% cream or Sarna Ultra Cream
MODERATE (CTCAE Grade 2)	
Dry Skin /	Emollients and topical as above plus Ammonium lactate or Urea 20%
Fissures	
Rash	Topical hydrocortisone 2.5% and/or clindamycin 1% gel plus doxycycline 100 mg b.i.d. or Minocycline 100 mg b.i.d.
Nail Changes	Vinegar soaks (dilute 1:1 white vinegar in water and soak fingers for 10 min a day)
Pruritus	H1-anti-histamines
SEVERE (CTCAE Grade 3 or 4)	
Dry Skin /	As above for Moderate
Fissures	
Rash	As above for Moderate plus Medrol dose pack
Nail Changes	Topical antibacterial / antifungal (ciclopirox) cream or Topical high potency steroids (clobetasol ointment) Consider dermatology consult for nail avulsion
Pruritus	Pregabalin 50-100 mg b.i.d.

Abbr.: b.i.d. = Twice daily, CTCAE = Common terminology criteria for adverse events.

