6.3.3 Other toxicities

Other toxicities that are not clearly attributable to copanlisib or fulvestrant, including overlapping toxicities, should be initially managed as follows:

- Treatment interruption or dose modification for Grade 1 or grade 2 AEs per CTCAE would be implemented at the investigator and patient's discretion.
- Both agents should be interrupted for Grade 3 AEs per CTCAE until the AEs have reached grade 1 or have returned to baseline. Following the resolution of toxicity, copanlisib may be resumed at the same dose level or at one or more dose levels lower, at the investigator's discretion. Fulvestrant should be resumed at the same dose level. Sequential reintroduction of each agent should be considered if clinically appropriate.
- Both agents should be interrupted for Grade 4 AEs per CTCAE until the AEs have reached grade 1 or have returned to baseline. For AEs that are not life-threatening and that can

Proprietary Information of MD Anderson

Protocol 2020-1241

19 October 2022

be managed, treatment with copanlisib may be resumed at a lower dose level, but fulvestrant should be resumed at the same dose level. Otherwise, patients must discontinue treatment. Sequential reintroduction of each agent should be considered if clinically appropriate.

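### Section 6.2 bars restart until toxicity is at Grade 1 or lower or baseline, while Tables 5, 6, 8 and 13 end the copanlisib hold for a Grade 3 event at Grade 2 or lower, and the visible text does not say which prevails

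*Combined protocol and SAP*

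**What the plan says.** **Section 6.2 (Dose Modification)** gives a general rule in two sentences. On holding: "the study drug deemed to be responsible for the AE will be held until AE resolves to grade 1 or baseline". On restarting: "When copanlisib or fulvestrant dosing is interrupted, either the patient must recover completely, or the toxicity must revert to NCI CTCAE" Grade 1 or lower, or baseline. It then says that patients whose Grade 3 or 4 event has not come down to that level within 4 weeks should be withdrawn. No toxicity type is excepted in the visible text.

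**Section 6.3.1, Tables 5 (nausea/vomiting), 6 (diarrhea) and 8 (neutropenia)** deal with copanlisib. In the Grade 3 row each holds the drug until toxicity is at or below "Grade 2. Resume at one dose level lower, if indicated".

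**Section 6.3.1.4**, in the dermatologic table captioned Table 13 (the section's text calls it Table 14), says for the first and second appearance of a Grade 3 event: "Interruption until Grade" 2 or lower, followed by a reduction of one dose level.

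**Section 6.3 (Toxicity Management)** introduces the tables: "These algorithms should be followed unless there are specific clinical circumstances for which the treating physician decides an alternative treatment approach is clinically appropriate".

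**Section 6.3.3** covers toxicities not clearly attributable to either drug and agrees with Section 6.2: "Both agents should be interrupted for Grade 3 AEs per CTCAE until the AEs have reached grade 1 or have returned to baseline".

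**The concern.** For a Grade 3 event that has fallen to Grade 2, one passage ends the copanlisib hold and another continues it. Section 6.2 uses mandatory language and contains no pointer to exceptions in the tables.

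The length of a hold matters beyond the patient's own management. Under Section 3.2, a related adverse event becomes a DLT if it prevents completion of the three Cycle 1 copanlisib doses, or if it delays the start of Cycle 2 by more than a week. Section 5 lets the study advance from Part 1 to Part 2 only if at most one DLT is seen. If the restart grade is left open, two investigators could treat the same clinical course differently, and one would record a DLT where the other would not.

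**Working it through.** No sample size, power or error rate is involved, so the check is a comparison of texts.

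**Step 1. Thresholds side by side for a Grade 3 event**

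| Place | Hold ends at | Agrees with 6.2? | A Grade 2 event on its own |
|---|---|---|---|
| Section 6.2 | Grade 1 or lower, or baseline | – | – |
| Table 5, nausea/vomiting | Grade 2 or lower | No | Held until Grade 1 or lower |
| Table 6, diarrhea | Grade 2 or lower | No | Held until Grade 1 or lower |
| Table 7, thrombocytopenia | Grade 1 or lower | Yes | No change |
| Table 8, neutropenia | Grade 2 or lower | No | No change |
| Table 13, dermatologic (1st and 2nd appearance) | Grade 2 or lower | No | No change |
| Section 6.3.3, other | Grade 1 or baseline | Yes | Discretionary |

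Four tables differ from Section 6.2. They also show no single intent. Tables 8 and 13 leave dosing unchanged for Grade 2 events. Tables 5 and 6 hold for a Grade 2 event, yet let a Grade 3 event that has fallen to Grade 2 resume. Table 7 leaves dosing unchanged at Grade 2 but requires Grade 1 after Grade 3. The intended threshold cannot be inferred from the pattern.

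**Step 2. Who is affected.** Three conditions must hold together: a Grade 3 event in one of the four groups; current toxicity at Grade 2 with baseline below Grade 2; and a copanlisib dose due. The four tables then end the hold, while Section 6.2 continues it.

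**Step 3. The 4-week sentence.** Suppose that such a patient resumes under a table and is still at Grade 2 at 4 weeks. The patient is then on treatment in line with the table, and at the same time meets the Section 6.2 withdrawal criterion. Giving the tables precedence on restart alone would not remove this second collision.

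**Step 4. DLT status in Part 1.** Under Section 3.2, for treatment-related events:

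- *Neutropenia.* Uncomplicated Grade 3 neutropenia is not a listed DLT. As an illustration, all three Cycle 1 doses are given, Grade 3 is found on Day 22, and the count is at Grade 2 when Cycle 2 is due on Day 29 (28 + 1). Table 8 permits Cycle 2 to start, so there is no DLT. Section 6.2 holds. If Grade 2 persists beyond Day 36 (29 + 7), the delay exceeds one week and the event is a DLT.
- *Nausea/vomiting and diarrhea.* A Grade 3 event that falls to Grade 2 or lower within 3 days of standard therapy is excepted. As an illustration, Grade 3 diarrhea falls to Grade 2 within that limit, just before the Day 8 dose. Table 6 permits the dose. Section 6.2 holds it, and if the dose is lost, Cycle 1 is incomplete and the excepted event becomes a DLT. Events slower than 3 days are DLTs under either rule.
- *Dermatologic.* A related Grade 3 skin event has no listed exception, so in Cycle 1 it is generally a DLT whichever restart grade applies.

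The DLT consequence therefore rests mainly on the first two groups.

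**Step 5. Search for a precedence rule.** The nearest text is the Section 6.3 sentence. It weighs the tables against the treating physician's judgment and does not mention Section 6.2.

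**The case against.** The strongest reply is that this is a general rule followed by specific ones. Section 6.3 requires the investigator to apply the dose modification guidelines, and says that the tables should be followed unless the physician decides otherwise. That is a natural reading, and it would be wrong to say that the protocol is silent. But Section 6.3 does not name Section 6.2. It also leaves untouched the 4-week sentence, which is written specifically for Grade 3 and 4 events and so is not merely a background default.

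A second reply is that a site can satisfy both sections by holding longer, since Section 6.3 allows departures from the tables. That is true for an individual patient, but the departure depends on specific clinical circumstances and is decided case by case. It does not give a uniform rule for counting DLTs.

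A third is that the copy is incomplete. A figure in Section 6.2 is not shown, and an exception there cannot be excluded. This stands: the absence of a precedence statement is established only for the visible text.

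Other limits also stand. A reader might infer that every Grade 3 event in the four groups is affected. That is not so: events that reach Grade 1 before the next dose are unaffected, as are patients whose baseline was Grade 2. A reader might also infer a conflict over fulvestrant, but these tables govern copanlisib only. The dose-interruption summaries in Section 8.1 are descriptive, so the effect there is slight.

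**Conclusion.** The inconsistency is real. As written, the Section 6.2 restart rule and the Grade 3 rows of Tables 5, 6, 8 and 13 give opposite default instructions for a copanlisib patient at Grade 2, above baseline, when a dose is due. If that patient resumes and remains at Grade 2, the 4-week withdrawal sentence conflicts as well.

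The reach is narrow, and the documents give no figure from which to estimate how often it would arise. In Part 1 the consequence is confined mainly to Grade 3 neutropenia, and to nausea/vomiting or diarrhea that meets the 3-day exception, where Grade 2 toxicity lasts long enough to lose a Cycle 1 dose or to delay Cycle 2 by more than a week. One such event can matter when at most one DLT is allowed. A reader might infer that skin events could be reclassified in the same way; Section 3.2 does not support that, because they are generally DLTs already.

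The conclusion assumes that the missing figure in Section 6.2 contains no exception or precedence statement. It implies nothing about which recovery grade is clinically right.

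**What to change.** Reconcile both Section 6.2 sentences, on restart and on 4-week withdrawal, with the Grade 3 rows of Tables 5, 6, 8 and 13. This can be done by aligning the recovery grade, or by adding a sentence that says which passage prevails and whether the 4-week sentence applies to patients who resumed under a table. The choice of grade belongs to the sponsor and the investigators.

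State that the same rule applies when deciding whether an incomplete Cycle 1 or a delayed Cycle 2 counts as a DLT. If Part 1 events have already been classified, check any that meet the conditions in Step 2 against the reconciled rule. Correct the reference to the dermatologic table at the same time.

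The cost is one or two clarifying sentences or a few table edits. No change to sample size or analysis follows.

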6.3 Toxicity Management

All dose modifications should be documented, including the approach taken and a clear rationale for the need for modification. For dose modification, the investigator must first assess if the toxicity is considered at least possibly related to the study treatment and must then apply the dose modification guidelines accordingly. Below are dose delay and management tables for the study drugs. These algorithms should be followed unless there are specific clinical circumstances for which the treating physician decides an alternative treatment approach is clinically appropriate. Consultation with the study chair is recommended.

6.3.1 Copanlisib toxicity management

Table 5: Management of Nausea/vomiting

Toxicity	Action to be Taken
CTCAE Grade 1	No change in dose
CTCAE Grade 2	Hold* until \leq Grade 1. No change in dose
CTCAE Grade 3	Hold* until \leq Grade 2. Resume at one dose level lower, if indicated.**
CTCAE Grade 4	Off copanlisib treatment

*Patients requiring a delay of >2 weeks may go off protocol therapy.
**Patients requiring >2 dose reductions should go off protocol therapy.

Recommended management: Antiemetics

Table 6: Management of Diarrhea

Toxicity	Action to be Taken
CTCAE Grade 1	No change in dose
CTCAE Grade 2	Hold* until \leq Grade 1. No change in dose
CTCAE Grade 3	Hold* until \leq Grade 2. Resume at one dose level lower, if indicated.**
CTCAE Grade 4	Off copanlisib treatment

*Patients requiring a delay of >2 weeks may go off protocol therapy.
**Patients requiring >2 dose reductions should go off protocol therapy.

Proprietary Information of MD Anderson

Protocol 2020-1241

19 October 2022

Recommended management: Loperamide antidiarrheal therapy

Dosage schedule: 4 mg at the first onset, followed by 2 mg with each loose motion until diarrhea-free for 12 hours (maximum dosage: 16 mg/24 hours)

Adjunct anti-diarrheal therapy is permitted and should be recorded when used.

Table 7: Management of thrombocytopenia

Toxicity	Action to be Taken
CTCAE Grade 1	No change in dose
CTCAE Grade 2	No change in dose
CTCAE Grade 3	Hold* until \leq Grade 1. Resume at one dose level lower, if indicated. **
CTCAE Grade 4	Off copanlisib treatment

*Patients requiring a delay of >2 weeks may go off protocol therapy.

**Patients requiring >2 dose reductions should go off protocol therapy.

Table 8: Management of Neutropenia

Toxicity	Action to be Taken
CTCAE Grade 1	No change in dose
CTCAE Grade 2	No change in dose
CTCAE Grade 3	Hold* until \leq Grade 2. Resume at one dose level lower, if indicated. **
CTCAE Grade 4	Off copanlisib treatment

*Patients requiring a delay of >2 weeks may go off protocol therapy.

**Patients requiring >2 dose reductions should go off protocol therapy.

